8.1.2. Relationship of Adverse Events to Study Drug

The relationship of AEs to study treatment will be assessed by the investigator as not related or related.

All TEAEs will be summarized by SOC, preferred term, relationship to study treatment, treatment, and overall. A subject with 2 or more events at each level of summarization will be counted once using the most related event. Events with missing relationship will be considered as related in the summaries but will be presented as missing in the data listings.

8.1.3. Severity of Adverse Event

The severity of an AE will be evaluated by the investigator as mild, moderate, or severe.

All TEAEs will be summarized by SOC, preferred term, severity, treatment, and overall. A subject with 2 or more events at each level of summarization will be counted once using the most severe event. Events with missing severity will be considered as severe in the summaries but will be presented as missing in the data listings.

8.1.4. Serious Adverse Events

An SAE is an AE occurring during any study phase (screening [from the time of signature of informed consent form], treatment, follow-up), that fulfils one or more of the following criteria:

- Results in death

- Is immediately life-threatening
- Requires in-patient hospitalization or prolongation of existing hospitalization
- Results in persistent or significant disability or incapacity
- Is a congenital abnormality or birth defect
- Is an important medical event that may jeopardize the subject or may require medical treatment to prevent one of the outcomes listed above.

All SAEs including death will be presented in a data listing.

8.1.5. Treatment-Emergent Adverse Events Leading to Study Discontinuation

All TEAEs leading to study discontinuation will be presented in a data listing.

8.2. Liver Events

The liver diagnostic investigations, liver risk factors/lift style events, and liver signs and symptoms data as collected in eCRF will be presented in data listings.

8.3. Clinical Laboratory Evaluations

The clinical chemistry, hematology, and urinalysis will be performed at visits specified in Appendix 14.1 SoA.

Other laboratory tests include testing for immunodeficiency virus (HIV), hepatitis B and C at screening, urine drug screen and alcohol screen at screening and on Day -1, pregnancy test at screening and on Day -1, and follicle stimulating hormone (FSH) testing in women at screening.

The details of clinical laboratory assessments to be performed are listed in Table 8-1.

Table 8-1 Laboratory Safety Variables

Hematology (whole blood)	White blood cell (WBC) count, red blood cell (RBC) count, hemoglobin (Hb), hematocrit (HCT), mean corpuscular volume (MCV), mean corpuscular hemoglobin (MCH), mean corpuscular hemoglobin concentration (MCHC), neutrophils absolute count, monocytes absolute count, eosinophils absolute count, basophils absolute count, platelets, and reticulocytes absolute count
Clinical chemistry (serum or plasma)	Alanine aminotransferase (ALT), aspartate aminotransferase (AST), alkaline phosphatase (ALP), gamma glutamyl transpeptidase (GGT), total bilirubin, unconjugated bilirubin, C-reactive protein (CRP), blood urea nitrogen, creatinine, glucose (fasting), albumin, phosphate, potassium, calcium, sodium, bicarbonate, thyroid stimulating hormone (TSH) ^a , thyroxine (T ₄) ^b , and follicle stimulating hormone (FSH) ^c
Urinalysis	Glucose, protein, hemoglobin, microscopy (if positive for blood or protein)
Viral serology	Human immunodeficiency virus (HIV I and II), hepatitis B surface antigen (HBsAg) and hepatitis C Virus antibody
Pregnancy test (females only)	Human beta chorionic gonadotrophin
Urine drug screen	Alcohol and cotinine, amphetamines (includes methamphetamine and ecstasy/3,4 methylenedioxymethamphetamine), barbiturates, benzodiazepines, cannabinoids (includes tetrahydrocannabinol), cocaine metabolites, methadone, tricyclic antidepressants, opiates (includes heroin, codeine, and oxycodone), and phencyclidine.

a Screening only

b Reflex only (if TSH is abnormal)

c Screening for post-menopausal women

The clinical laboratory that will perform the tests will provide the reference ranges for all clinical laboratory parameters. Abnormal clinical laboratory values will be flagged as either high or low (or normal or abnormal) based on the reference ranges for each laboratory parameter and evaluated as clinically significant or not clinically significant by the investigator. All laboratory results along with the abnormal flag and clinical significance will be presented in data listings. The potentially clinically significant (PCS) values will also be flagged. The PCS criteria are defined in Appendix 14.2.

Actual results and changes from baseline will be summarized for hematology, chemistry, quantitative urinalysis laboratory tests by treatment and visit. Shift tables with categories of low, normal, and high for quantitative results, and normal and abnormal for qualitative results will be provided by treatment and visit.

8.4. Testosterone, Luteinizing Hormone, Follicle Stimulating Hormone, and Inhibin B Assessments

For Cohorts 4 to 6, in order to monitor for effects on testicular function in male subjects, samples for assessment of testosterone, LH, FSH, and inhibin B levels will be collected at 0 hour (0800 or 1000) and at 4, 6, 8, 12, and 22 hours on Day -1 and at 0 hour (0800 or 1000) and at 1, 2, 4, 6, 8, 12, 24, 36, 48, and 72 hours on Day 1, as listed in the SoA (Appendix 14.1).

The results of these assessments will be presented in a data listing for safety population.

8.5. Vital Sign Measurements

Vital signs will be measured at specified timepoints in Appendix 14.1. Height will be measured at screening, and weight and BMI will be measured/calculated at specified timepoints in Appendix 14.1 SoA.

Vital signs will include systolic and diastolic blood pressure (BP), pulse rate (PR), respiratory rate (RR), and body temperature. Vital signs will be measured in a semi-supine position after 5 minutes rest. Supine and standing BP and PR will be measured using a semiautomatic recording device. Supine BP and PR will be taken after at least 5 minutes supine rest. Standing BP and PR will be taken approximately 3 minutes after the respective supine measurements. Three consecutive BP readings will be recorded at intervals of at least 1 minute. The average of the 3 BP readings will be recorded on the eCRF, and these records will be used in statistical summaries.

Orthostatic BP will be calculated as:

$$\text{BP in supine position} - \text{BP in standing position}$$

Orthostatic PR will be calculated as:

$$\text{PR in standing position} - \text{PR in supine position}$$

Actual results and changes from baseline in vital sign, weight, and BMI measurements will be summarized by treatment and timepoint. Vital sign measurements including the orthostatic BP and orthostatic PR, weight, and BMI results., along with PCS flags will be presented in a data listing. The PCS criteria are defined in Appendix 14.3.

8.6. Electrocardiograms

Twelve-lead paper ECGs (pECG) allow the investigator to review the ECG tracings at bedside and determine any potential risks. Digital 12-lead ECGs (dECG) are collected and electronically

submitted to the AstraZeneca ECG Center for expert review and reporting of ECG intervals. Telemetry is used for continuous monitoring of ECG activity as a safety measure.

8.6.1. Twelve-Lead Paper ECG

Twelve-lead pECGs will be obtained after the subject has been resting in the supine position for at least 10 minutes at specified timepoints in Appendix 14.1 SoA. All pECGs will be evaluated for heart rate, PR, RR, QRS, QT, and QTcF intervals. The Investigator will judge the overall interpretation as normal or abnormal. If abnormal, it will be decided whether or not the abnormality is clinically significant or not clinically significant, and the reason for the abnormality will be recorded in the eCRF.

All pECG data including investigator findings will be presented in a listing.

8.6.2. Digital ECG

The AstraZeneca ECG Center will perform the digital ECG (dECG) analysis and interpretation in this study, using the EClysis[®] system, version 4.0, or higher. The following dECG variables will be reported by the AstraZeneca ECG Center: RR, PR, QRS and QT intervals from the lead defined as the primary analyses lead. Heart rate will be derived as 60/(RR in seconds) and QTcF will be derived as QT (msec)/(RR in seconds)^{1/3}.

The dECG data will be smoothed on an individual subject basis before performing the derivations above and before calculation of any changes from baseline or descriptive statistics. For each subject it will be done as follows: the mean value of all the measurements will be taken for nominal time-point recordings. At least 4 measurements with the time between the first and last record greater than 2.75 minutes for a nominal time-point should be present or else, the smoothed value at the corresponding nominal time-point will be set to missing.

Digital ECG results will be listed by treatment (pooled placebo, dose level of AZD4041) for each subject and time-point and will include all individual and smoothed values of PR, RR, QRS, QT interval and the derived values of QTcF and HR. The changes from baseline for smoothed and derived parameters will be listed as well.

Descriptive statistics of smoothed PR, RR, QRS, QT values and derived QTcF and HR values as well as change from baseline will be summarized by treatment group (pooled placebo, dose level of AZD4041, and pooled AZD4041) and nominal time-point. The baseline for the dECG measurements will be the smoothed pre-dose assessment on Day 1.

The number and percent of subjects whose worst (i.e. highest) post-baseline smoothed QTcF value, according to the following categories, will be tabulated by visit, timepoint, and treatment group (pooled placebo, dose level of AZD4041, and pooled AZD4041):

- Absolute value >450 msec and ≤ 480 msec
- Absolute value >480 msec and ≤ 500 msec
- Absolute value >500 msec
- Increase from baseline >30 msec and ≤ 60 msec

- Increase from baseline >60 msec

The above tabulations will be presented separately for the subgroups who have an elevated QTcF (>450 msec) at baseline and those who do not.

All dECG data will be presented in a listing.

8.6.3. Telemetry

To allow a real-time assessment of cardiac safety at the study site, subjects will be monitored by telemetry (for real-time assessment of cardiac rate and rhythm) for 4 to 6 hours at specified timepoints in Appendix 14.1 SoA. Any clinically significant change noted on telemetry will be followed up with a 12-lead ECG. Further evaluation and treatment will be performed as deemed appropriate by the Investigator. The telemetry monitoring data as collected in eCRF will be presented in a data listing.

8.7. Physical Examination

Physical examination will be conducted at specified timepoints in Appendix 14.1 SoA.

A complete physical examination will be performed and includes an assessment of the following systems: cardiovascular, chest/lungs/respiratory, gastrointestinal, thyroid/neck, lymphatics, dermatological/skin, musculoskeletal/extremities, neurological, and head/ears/eyes/nose/throat (including mouth).

Physical examination results will be presented in a data listing.

9. Pharmacokinetics

9.1. Data Handling

Plasma concentrations that are below the limit of quantification (BLQ) will be treated as zero for calculation of descriptive statistics. When all concentrations are BLQ for a timepoint, mean BLQ concentrations will be presented as BLQ, and the SD and CV will be reported as not applicable, otherwise the calculated mean will be presented.

For PK parameter calculations, BLQ values will be treated as zero with the exception that a BLQ value between 2 quantifiable concentrations will be set as missing. If consecutive BLQ concentrations are followed by quantifiable concentrations in the terminal phase, those concentrations after BLQ concentrations will be treated as missing.

Missing concentrations will be excluded from summaries and PK parameter calculations.

9.2. Plasma Concentration

Blood samples for the determination of plasma concentrations of AZD4041 will be collected on Day 1 at the following time points: predose (0), and at 0.25, 0.5, 1, 1.5, 2, 3, 4, 6, 8, 12, 24, 36, and 48 hours postdose. For Cohorts 4 to 6, an additional blood sample will be collected at 72 hours postdose.

Pharmacokinetic collections that have an actual sampling time that deviates from the nominal collection time more than 10% will be flagged in the data listing, but the nominal sampling time will be used for summarization.

AZD4041 plasma concentration data will be summarized using descriptive statistics (number of subjects, number of nonmissing values, arithmetic mean, SD, CV, median, minimum, and maximum) by treatment and nominal sampling time. Individual and mean AZD4041 plasma concentration versus time data will be plotted by treatment. For ease of presentation, mean plasma concentrations of AZD4041 will be plotted by nominal time by treatment on both linear and semi-logarithmic scales.

Plasma PK concentrations of AZD4041 will be reported to the precision of the raw data in listing presentations; summary statistics for arithmetic mean, median, minimum, maximum, and SD will be reported to 3 significant figures; and CV will be reported to 1 decimal place.

9.3. Pharmacokinetic Parameters

The plasma concentration-time data for AZD4041 will be analyzed by non-compartmental analysis using Phoenix® WinNonlin® (Certara USA, Inc., Princeton, NJ) Version 8.0 or higher. Actual sampling times will be used for the estimation of all plasma PK parameters.

If data allow, the following PK parameters will be calculated:

Pharmacokinetic parameters:

PK Parameter	Definition
C_{\max}	Maximum (peak) plasma drug concentration
T_{\max}	Time to reach maximum (peak) plasma concentration following drug administration
AUC_{0-t}	Area under the curve from time 0 to time t
$AUC_{0-\infty}$	Extrapolation of the area under the curve from time 0 to infinity, calculated as $AUC_{0-\infty} = AUC_{0-t} + C_{\text{last}}/\lambda_z$, where C_{last} is the last quantifiable plasma drug concentration
$t_{1/2 \lambda_z}$	Terminal half-life, calculated as: $t_{1/2} = \ln(2)/\lambda_z$
CL/F	Apparent total clearance of the drug from plasma after oral administration, calculated as: $CL/F = \text{Dose}/AUC_{0-\infty}$
V_{ss}/F	Apparent volume of distribution at steady state

In addition to the above PK parameters, which will be listed and summarized, the following parameters will also be listed to document the selection of data points used to estimate $t_{1/2}$ using non-compartmental procedures:

%AUC _{extrap}	Percentage of the area extrapolated for calculation of AUC _{0-∞} .
λ_z	Apparent terminal elimination rate constant, where λ_z is the magnitude of the slope of the linear regression of the log concentration versus time profile during the terminal phase.
Number of points	Number of data points used to estimate λ_z ; a minimum of 3 data points must be used, and C_{max} must not be included.
λ_z lower	Lower bound used for the estimation of λ_z .
λ_z upper	Upper bound used for the estimation of λ_z .
Rsq	r^2 , the coefficient of determination (goodness of fit statistic); visual inspection of the terminal slope will be performed. In general, λ_z may only be retained if $r^2 \geq 0.80$

Plasma PK parameters for AZD4041 will be presented in data listings and summarized by treatment using descriptive statistics (number of subjects, arithmetic mean, SD, CV%, median, geometric mean, geometric CV%, minimum, and maximum) by treatment regimen. T_{max} will be summarized using the descriptive statistics median, minimum, and maximum only.

Plasma PK parameters of AZD4041 will be displayed to 3 significant figures in all data listings and summary tables, with exception of time variables (T_{max} , λ_z lower, and λ_z upper) which will be displayed to 2 decimal places.

9.4. Pharmacokinetic Statistical Analysis

Dose-proportionality for AZD4041 will be evaluated for C_{max} , AUC_{0-t} and AUC_{0-inf}. A power model will be fitted to describe the relationship between Y (C_{max} , AUC_{0-t} and AUC_{0-inf}) and X (dose) using the least-squares linear regression model, $\ln(Y) = \ln(\alpha) + \beta \ln(X)$, which is the logarithmic form of $Y = \alpha X^\beta$.

The intercept of regression line, $\ln(\alpha)$, and the slope of the regression line, β , will be presented along with the 90% confidence interval (CI) of the slope. Dose-proportionality will be concluded if the 90% CI of the slope β lies entirely within $[1+\ln(0.8)/\ln(r), 1+\ln(1.25)/\ln(r)]$, where r is a ratio that describes the dose range and is defined as the ratio of highest dose/lowest dose ([Smith et al 2000](#)). If the proportionality is not demonstrated over the entire dose range, the lowest or highest dose will be removed, and the analysis will be repeated until a range of proportionality is determined. Dose proportionality will be assessed with at least 3 dose levels.

The statistical analyses will be based on the PK population.

10. Pharmacodynamics

To characterize the PD relationship between drug exposure and QT interval, an exposure-response (E-R) analysis may be conducted with data from this study alone or in combination with other studies as appropriate, with a pre-specified workflow described in a separate technical document for the QTcF parameter, as part of the cardiac safety evaluation and with the intention to obtain a Thorough QT study substitute. The results of the E-R analysis will be presented in an E-R Analysis Report and may not be included in the main study report. The specification of the E-R analysis (the E-R analysis plan) is not included in this statistical analysis plan (SAP).

11. Interim Analysis

No formal interim analysis is planned for this study.

The SRC will review data from each cohort before progression to the next cohort can occur. The blinded safety, PK concentration, and PK parameter data will be reviewed by the investigators, medical monitor, and sponsor's representative as described in the SRC plan to ensure that it is safe to proceed with the planned dose escalation.

12. Changes in the Planned Analysis

There are no changes in this statistical analysis plan compared to the protocol.

13. References

Boutrel et al 2005

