For cohorts 1, 2 and 3 the predicted exposure was planned not exceed a limit that is approximately 10-fold below the NOAEL exposures in males in the Dog 28-day study (Table 4). Subsequent cohorts in females of non-childbearing potential and vasectomised males have revised exposure limits that is proposed not to exceed the intermediate dose NOAEL exposures in the female dog at [REDACTED]. Utilizing geometric mean data, observed exposures at [REDACTED] provide a [REDACTED] margin to free C_{max} and an [REDACTED] margin to free AUC_{0-inf} when compared to the female dog NOAEL derived from the 28 Day GLP toxicology study (Table 5). For the partial Cohort 5 data at [REDACTED] geometric mean data indicates a [REDACTED] margin to free C_{max} and an [REDACTED] margin to free AUC_{0-inf} when the same comparison is made to the female dog NOAEL exposures.

Table 4 Observed exposures and margins to male dog NOAEL

Clinical dose (mg)	Human free C_{max} (ng/mL)	Human free $C_{max}/Dose$	C_{max} margin to male dog NOAEL	Human free AUC_{0-inf} (ng·h/mL)	Human free $AUC_{0-inf}/Dose$	AUC_{0-inf} margin to male dog NOAEL
[REDACTED]	[REDACTED]	[REDACTED]	[REDACTED]	[REDACTED]	[REDACTED]	[REDACTED]
[REDACTED]	[REDACTED]	[REDACTED]	[REDACTED]	[REDACTED]	[REDACTED]	[REDACTED]
[REDACTED]	[REDACTED]	[REDACTED]	[REDACTED]	[REDACTED]	[REDACTED]	[REDACTED]

AUC_{0-inf} Extrapolation of the area under the curve from time 0 to infinity; C_{max} Maximum (peak) plasma drug concentration; NOAEL No-observed-adverse-effect level

n/a = not applicable since male dog NOAEL was not utilized as exposure limit beyond Cohort 3

Note: Exposures are provided as geometric means (n=6).

Pharmacokinetic data within cohorts indicated that there was some variability in systemic exposure between individuals. As an example in Cohort 3, the coefficient of variation for C_{max} geometric mean was 24.7% and the coefficient of variation for AUC_{0-inf} geometric mean was 43.7%. For 3 subjects within Cohort 3, extrapolation of AUC_{0-inf} following noncompartmental analysis was >20%, indicating some uncertainty in the calculation of this parameter. However, with an extended sampling period and extrapolation of AUC_{0-inf} following noncompartmental analysis of <20% in all subjects, variability in systemic exposure was still evident in Cohort 4, as exemplified by a coefficient of variation for C_{max} geometric mean of 21.2% and a coefficient of variation for AUC_{0-inf} geometric mean of 52.4%.

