3.2. Study Endpoints

3.2.1. Primary Endpoints

Safety endpoints include the following:

- The frequency and severity of adverse events (AEs)
- Clinical laboratory test results (hematology, biochemistry, and urinalysis)
- Vital sign measurements (systolic and diastolic blood pressure, pulse rate, respiratory rate, and body temperature)
- 12-Lead ECG (paper ECG and digital ECG) and telemetry results
- Testosterone, luteinizing hormone (LH), follicle stimulating hormone (FSH), and inhibin B (male subjects in Cohorts 4, 5, and 6 only)

PK endpoints include the following:

- Maximum (peak) plasma drug concentration (C_{max})
- Time to reach maximum (peak) plasma concentration following drug administration (T_{max})
- Area under the plasma concentration versus time curve from time zero to the last quantifiable concentration in plasma (AUC_{0-t})
- Extrapolation of the area under the curve from time 0 to infinity (AUC_{0-inf})
- Terminal half-life ($t_{1/2\lambda_z}$)
- Apparent total clearance of the drug from plasma after oral administration (CL/F)
- Apparent volume of distribution at steady state after oral administration (V_{ss}/F)

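### The AUC0-t power model mixes cohorts sampled to 48 h with cohorts sampled to 72 h, which pushes the dose-proportionality slope above 1 for a proportional drug

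*SAP*

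**What the plan says.** SAP 9.4: "Dose-proportionality for AZD4041 will be evaluated for" Cmax, AUC0-t and AUC0-inf, by least-squares regression of the log parameter on log dose. The rule reads "Dose-proportionality will be concluded if the 90% CI of the slope" lies within 1 + ln(0.8)/ln(r) to 1 + ln(1.25)/ln(r), where r is the highest dose divided by the lowest. The slope and its 90% CI are to be presented. If the full range fails, "the lowest or highest dose will be removed, and the analysis will be repeated until a range of proportionality is determined", with at least three dose levels kept.

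SAP 3.2.1 defines AUC0-t as "Area under the plasma concentration versus time curve from time zero to the last quantifiable concentration in plasma". SAP 9.3 adds no fixed end time.

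SAP 9.2 puts the post-dose samples for all cohorts at "0.25, 0.5, 1, 1.5, 2, 3, 4, 6, 8, 12, 24, 36, and 48 hours postdose" and then adds: "For Cohorts 4 to 6, an additional blood sample will be collected at 72 hours postdose". The schedules of activities in both documents agree.

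Protocol 2.3 reports that three Cohort 3 subjects had more than 20% of AUC0-inf extrapolated, "indicating some uncertainty in the calculation of this parameter". With the extended sampling, every Cohort 4 subject was below 20%.

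Neither document defines a partial AUC over a common window, a model term for the sampling window, or a sensitivity analysis on this point.

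**The concern.** In an ascending-dose study the longer window falls on the higher doses. Area between 48 and 72 h is counted in Cohorts 4 to 6 and left out in Cohorts 1 to 3. The regression has only log dose to explain that step, so the slope absorbs it. The Cohort 3 and 4 extrapolation figures indicate that the area beyond 48 h is not trivial for this drug.

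AUC0-t is a primary PK endpoint in SAP 3.2.1, and its slope will be reported and judged against limits of its own. The risk is a reported slope that suggests more-than-proportional exposure when the cause is the sampling schedule. A second risk is a dose-removal sequence steered partly by that artefact.

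**Working it through.** The plan states no slope, power or expected width for this analysis, so there is no figure of its own to reproduce.

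**Inputs from the documents.** Last sample 48 h (Cohorts 1 to 3) or 72 h (Cohorts 4 to 6): SAP 9.2. Six active subjects per cohort, 36 in all: SAP 3.1. CV of AUC0-inf 43.7% (Cohort 3) and 52.4% (Cohort 4), and the extrapolation pattern: Protocol 2.3. Acceptance limits: SAP 9.4.

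**Assumptions.** Doses ascend by cohort and are equally spaced on the log scale; decline is mono-exponential; concentrations are quantifiable to the last sample. Since doses are redacted, r is varied. One value, 471/13 = 36, comes from the predicted Cmax margins in Protocol 4.3 and is only one point in the range.

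**1. Step between the two windows.** Let p48 be the fraction of AUC0-inf beyond 48 h. Under mono-exponential decline p72 = p48^1.5, and

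step = ln[(1 − p72)/(1 − p48)].

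**2. Slope bias.** Scale log dose to x = 0, 0.2, 0.4, 0.6, 0.8, 1, and let s = 0, 0, 0, 1, 1, 1 mark the 72 h cohorts. Then Σ(x − 0.5)s = 0.1 + 0.3 + 0.5 = 0.9 and Sxx = 2(0.25 + 0.09 + 0.01) = 0.70, so the coefficient is 0.9/0.70 = 1.286 and

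bias = 1.286 × step / ln r.

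The acceptance half-width is ln(1.25)/ln r = 0.2231/ln r. In the ratio of the two, ln r cancels.

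| Beyond 48 h | Beyond 72 h | Step | Bias as share of half-width | Bias, r = 10 | r = 36 | r = 100 |
|---|---|---|---|---|---|---|
| 10% | 3.2% | 0.073 | 42% | 0.041 | 0.026 | 0.020 |
| 15% | 5.8% | 0.103 | 59% | 0.057 | 0.037 | 0.029 |
| 20% | 8.9% | 0.129 | 75% | 0.072 | 0.046 | 0.036 |
| 30% | 16.4% | 0.177 | 102% | 0.099 | 0.064 | 0.049 |

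With unequal steps of 1.3- to 4-fold, the share is 51 to 62% at 15% and 64 to 79% at 20%. With first-order absorption (ka 1/h) added, it is 9% for a half-life of 8 h, 30% at 12 h, 78% at 20.7 h and 113% at 30 h.

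**3. Which row fits the data.** Of the half-lives tried, about 17 to 17.5 h makes the joint Cohort 3 and Cohort 4 pattern most likely (probability 10 to 13%). That is about 15% beyond 48 h. At 20.7 h, about 20% beyond 48 h, the probability is 6 to 9%.

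**4. Simulation under true slope 1.** 4,000 trials per setting, 36 active subjects, one compartment, SAP sampling times, linear trapezoid (the SAP names no rule), λz from the last three points, clearance CV 43.7% or 52.4%, volume CV 20%, ka 1/h, r from 10 to 100.

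| | 15% beyond 48 h: AUC0-t | AUC0-48 | 20% beyond 48 h: AUC0-t | AUC0-48 |
|---|---|---|---|---|
| Estimate above upper limit | 30–35% | 5–9% | 38–42% | 4–7% |
| 90% CI wholly above 1 | 20–26% | 5–6% | 28–37% | 5% |
| Proportionality concluded, full range | 0.1–0.8% | 0.6–5% | 0.1–1.8% | 2–12% |

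At 15% the mean AUC0-t slope is 1.03 to 1.07. The mean AUC0-inf slope is 1.001 to 1.005.

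**5. Dose removal.** Recomputing the coefficient for reduced ranges gives 1.2 (Cohorts 1–5, 2–6, 2–5), 1.0 (2–4, 3–5), 0.9 (1–4, 3–6) and 0 (1–3, 4–6). Ranges that still span Cohorts 3 and 4 therefore keep 0.9 to 1.2 × 0.103/0.2231, or 41 to 55% of the half-width at 15%, and 52 to 70% at 20%. The bias vanishes only when the range lies wholly on one side of the change in sampling.

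**The case against.** The strongest reply is that little turns on this slope. The SAP decides on the CI lying within limits, not on the point estimate or on a CI above 1, and on that criterion most trials fail with either window. With removal carried through to the widest passing range of at least three doses, some range passes in 0.7 to 8% of simulated trials as written and in 2.6 to 28% with AUC0-48. The exposure margins in Protocol 2.3 and 4.3 use free Cmax and AUC0-inf, and the projection for dose selection is a separate regression. AUC0-inf sits in the same SAP analysis almost unbiased. The protocol synopsis lists PK as secondary, although its Table 6 and the SAP make it primary. All of this stands and limits the severity. It does not remove the point, because the AUC0-t slope and CI will be reported and read, and a conflict with AUC0-inf has no stated resolution.

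The size does depend on unseen inputs. At a half-life of about 8 h the bias would be negligible, and the Safety Review Committee may repeat or lower a dose, which would break the ascending order. The Cohort 3 extrapolation argues against so short a half-life, but it comes from six subjects.

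AUC0-48 also has a cost: it blunts late non-linearity. If clearance fell 30% from a 17 h half-life, AUC0-inf would rise 43% (1/0.7) but AUC0-48 only 24%, about 60% of the log departure (ln 1.24/ln 1.43). That is a good reason to keep AUC0-inf in the model alongside it. It is not a reason to keep a variable whose window changes with dose.

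**Conclusion.** The concern holds. As written, the AUC0-t power model has an expected slope above 1 under true proportionality, provided that doses ascend by cohort and drug is quantifiable beyond 48 h. The plausible bias is about 59 to 75% of the acceptance half-width (15 to 20% of area beyond 48 h), within a wider range of 42 to 102%. The direction follows from the documents. Confidence in the size is medium, because doses, half-life and quantification limit are not available.

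The damage is to the reported slope and to any apparent more-than-proportional finding. The artefact is not the main reason the criterion would fail: with CVs of 44 to 52% and 36 active subjects, the CI is usually too wide in any case. The slope should be corrected before the SAP is applied, but the point does not bear on subject safety.

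**What to change.** In SAP 9.3 and 9.4, define AUC0-48 for all cohorts and use it in place of AUC0-t in the power model.

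- Before fitting, check that 48 h samples are quantifiable in the lowest-dose cohorts. SAP 9.1 says "For PK parameter calculations, BLQ values will be treated as zero", so a 48 h value below the limit at the lowest dose alone would leave a bias of 14 to 17% of the half-width, and at the two lowest doses 22 to 27%. If the check fails, use for every cohort the latest nominal time that is quantifiable there.
- Keep AUC0-t in the descriptive tables, with a note that its window differs between Cohorts 1 to 3 and 4 to 6.
- Keep AUC0-inf in the model with all profiles. The SAP has no rule excluding profiles with more than 20% extrapolated, and none should be added to the main fit. It would drop slow eliminators mainly from the 48 h cohorts, and in simulation it moves the AUC0-inf slope from about 1.00 to 1.05–1.07 at r = 36. Any such run should be labelled supportive.

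The cost is SAP wording and one partial-AUC parameter, with no new samples.
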